**Table 5.1      Planned Dose Cohorts**

Cohort	eGFR	VFI Dose	Number of Doses	Comparator Dose	Number of Doses	Number of Subjects
1*	≥ 60 mL/min/1.73 m 	47 mg/3 mL	1	---	---	Up to 8
2	≥ 60 mL/min/1.73 m 	47 mg/3 mL	2	Iohexol 5 mL	1	Up to 8
3	≥ 30 and < 60 mL/min/1.73 m 	47 mg/3 mL	1	Iohexol 5 mL	1	Up to 8
4	≥ 15 and < 30 mL/min/1.73 m 	47 mg/3 mL	1	Iohexol 5 mL	1	Up to 8

\*Subjects in Cohort 1 will receive a volume challenge

Cohort 1:

Eligible subjects ≥ 50 kg in weight will receive a single dose of VFI followed 130 minutes later by a 350 mL infusion of 5% albumin over 30 minutes on Day 1. Eligible subjects < 50 kg in weight will receive a single dose of VFI followed 130 minutes later by a maximum infusion of 5% albumin of 7 mL/kg over 30 minutes on Day 1. Subjects will remain resident in the CRU for at least 24 hours after VFI administration for safety, PK, and PD assessments. Subjects will return to the CRU for an end-of-study (EOS) visit on Day 21 (± 1 day).

Cohort 2:

Eligible subjects will receive a dose of VFI followed 160 minutes later by a single dose of Iohexol on Day 1 and a second dose of VFI 24 hours following the initial dose of VFI. Subjects will remain resident in the CRU for at least 24 hours after the second VFI administration for safety, PK, and PD assessments. Subjects will return to the CRU for follow-up visits on Days 5 (± 1 day), 9 (± 1 day), and 16 (± 1 day) and an EOS visit on Day 22 (± 1 day).

Cohorts 3 and 4:

Eligible patients will receive a single dose of VFI followed 160 minutes later by a single dose of Iohexol on Day 1.

Patients enrolled into Cohort 3 at ICON Early Phase Services will remain resident in the CRU for at least 24 hours after VFI administration for safety, PK, and PD assessments. Patients will return to the CRU for follow-up visits on Days 4 (± 1 day), 8 (± 1 day), and 15 (± 1 day), and an EOS visit on Day 21 (± 1 day).

Patients enrolled into Cohorts 3 or 4 at UAB will remain in the CRU through the 12-hour sample collection after VFI administration for safety, PK, and PD assessments. Patients will stay at a local hotel near the CRU and will return to the CRU on Day 2 for 24-hour sample collection. Patients will return to the CRU for follow-up visits on Days 4 (± 1 day), 8 (± 1 day), and 15 (± 1 day), and an EOS visit on Day 21 (± 1 day).

Refer to [Table 2.1](#), [Table 2.2](#), and [Table 2.3](#) for the Schedules of Assessments and Procedures.

CONFIDENTIAL

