## 8.6 Safety Assessments

### 8.6.1 Adverse Events

Subjects will be monitored for AEs from administration of the first dose of study drug through the EOS visit. Refer to [Section 9](#) for additional details.

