**Table 8.3 Clinical Laboratory Tests**

Hematology	Coagulation	Serum Chemistry	Urinalysis a,b,e
Hematocrit	INR c	Sodium	Nitrites
Hemoglobin		Potassium	Leukocytes
Red blood cell count		Chloride	Protein
Mean corpuscular volume		Albumin	Glucose
White blood cell count		Aspartate aminotransferase	Ketones
Platelet count (estimate not acceptable)		Alanine aminotransferase	Urobilinogen
Neutrophils (absolute)		Alkaline phosphatase	Bilirubin
Eosinophils (absolute)		Creatine phosphokinase	Blood
Basophils (absolute)		Glucose d	pH
Lymphocytes (absolute)		Total cholesterol d	Specific gravity
Monocytes (absolute)		BUN	
		Creatinine	
		Total bilirubin	
		Calcium	
		Total protein	
		Phosphorous	

- a. In case of clinically significant findings, a microscopic analysis will be performed.
- b. If 1+ or greater protein is noted in the urinalysis, a calculated urine protein to creatinine ratio will be performed.
- c. Cohorts 3 and 4 only.
- d. Should be collected after fasting for a minimum of 8 hours.
- e. A urine protein to creatinine ratio will be performed only at predose on testing day and 24 hours postdose. Subjects will be fasting prior to this measurement.

For any laboratory test value outside the reference range that the investigator considers clinically significant during the on-study period (ie, following dose administration), the investigator will:

- Repeat the test to verify the out-of-range value and clinical significance.

CONFIDENTIAL

- Follow the out-of-range value to a satisfactory clinical resolution.
- Record as an AE any laboratory test value that (1) is confirmed by repeat and the investigator considers clinically significant, (2) requires a subject to be discontinued from the study, (3) requires a subject to receive treatment, or (4) requires a change or discontinuation of the study drug (if applicable).

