6 STUDY DESIGN

6.1 General

This is a Phase 2b, prospective, open-label study designed to evaluate the safety, tolerability, PK, and PD of FAST PV and mGFR Technology in healthy subjects and patients with varying degrees of renal impairment.

For Cohorts 1 and 2, administration of the study drug will occur within 21 days of screening. Eligible subjects/patients will be admitted to the CRU on Day -1, at which time assessments will be performed, and results from both screening and Day -1 (inclusion/exclusion criteria, body weight, height [screening only], body mass index [BMI], medical and surgical history, physical examination, vital signs and pulse oximetry, 12-lead ECG, clinical laboratory tests, renal function assessment, follicle-stimulating hormone [FSH; screening only] and pregnancy test [females only], urine drugs of abuse, and serum alcohol screen) will be reviewed to confirm eligibility.

For Cohorts 3 and 4, administration of the study drug will occur within 21 days of screening. Eligible subjects/patients will be admitted to the CRU on Day 1, at which time assessments will be performed and results from both screening and predose administration testing (inclusion/exclusion criteria, body weight, height [screening only], BMI, medical and surgical history, physical examination, vital signs and pulse oximetry, 12-lead ECG, clinical laboratory tests, renal function assessment, FSH and pregnancy test [screening only], urine drugs of abuse, and serum alcohol screen) will be reviewed to confirm eligibility.

Cohort 1:

Eligible subjects \geq 50 kg in weight will receive a single dose of VFI followed 130 minutes later by a 350 mL infusion of 5% albumin over 30 minutes on Day 1. Eligible subjects $<$ 50 kg in weight will receive a single dose of VFI followed 130 minutes later by a maximum infusion of 5% albumin of 7 mL/kg over 30 minutes on Day 1. Subjects will remain resident in the CRU for at least 24 hours after VFI administration for safety, PK, and PD assessments. Subjects will return to the CRU for an end-of-study (EOS) visit on Day 21 (\pm 1 day).

Cohort 2:

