Eligible subjects will receive a dose of VFI followed 160 minutes later by a single dose of Iohexol on Day 1 and a second dose of VFI 24 hours following the initial dose of VFI. Subjects will remain resident in the CRU for at least 24 hours after the second VFI administration for safety, PK, and PD assessments. Subjects will return to the CRU for follow-up visits on Days 5 (\pm 1 day), 9 (\pm 1 day), and 16 (\pm 1 day) and an EOS visit on Day 22 (\pm 1 day).

Cohorts 3 and 4:

Eligible patients will receive a single dose of VFI followed 160 minutes later by a single dose of Iohexol on Day 1. Patients will remain in the CRU through the 12-hour sample collection after VFI administration for safety, PK, and PD assessments. Patients will stay at a local hotel near the CRU and will return to the CRU on Day 2 for the 24-hour sample collection. Patients will return to the CRU for follow-up visits on Days 4 (± 1 day), 8 (± 1 day), and 15 (± 1 day) and an EOS visit on Day 21 (± 1 day).

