10.1.11.2 Adverse Events

All AEs will be coded to system organ class (SOC) and preferred term (PT) using Medical Dictionary for Regulatory Activities (MedDRA Version 20.0 or higher) and presented by subject in data listings.

Adverse events with onset on or after the first dose of study drug, or with an onset before the first dose of study drug that increase in severity on or after the first dose of study drug, will be considered treatment-emergent.

The overall incidence of TEAEs (number and percentage of subjects) as well as the number of events will be summarized by cohort (and overall), mild, moderate or severe TEAE, serious TEAE, possibly or probably related TEAE, TEAEs leading to study drug discontinuation, and serious TEAEs resulting in death.

The TEAEs will be summarized and tabulated at both the subject (number [%] of subjects) and event (number of events) level:

- By cohort, SOC, and PT
- By cohort, SOC, PT, and maximum reported severity
- By cohort, SOC, PT, and maximum relationship to study drug

For the incidence at the subject level by SOC and PT, if a subject experiences more than 1 event within the same SOC and PT, only one occurrence will be included in the incidence.

For the incidence at the subject level by SOC, PT, and severity, if a subject experiences more than one event within the same SOC and PT, only the most severe occurrence will be included in the incidence.

For the incidence at the subject level by SOC, PT and relationship to study drug; if a subject experiences more than one event within the same SOC and PT, only the most closely related occurrence will be included in the incidence.

Any SAEs, AEs with outcome of death, or AEs resulting in discontinuation of study or study drug will be listed separately.

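### TEAE rates by cohort and overall mix in visit frequency: after discharge Cohort 1 has one scheduled visit, Cohorts 2–4 have four, and the SAP does not separate the periods

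*SAP*

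**What the plan says.** **TEAE display.** SAP 10.1.11.2 defines treatment-emergent events to include "Adverse events with onset on or after the first dose of study drug", with no upper limit and no division into periods. On the display it says: "The overall incidence of TEAEs (number and percentage of subjects) as well as the number of events will be summarized by cohort (and overall". Tables 14.3.1.1 to 14.3.1.4 follow from this.

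**AE collection.** Protocol 8.6.1: "Subjects will be monitored for AEs from administration of the first dose of study drug through the EOS visit". The nominal window is about three weeks in every cohort.

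**Visits after discharge (SAP 6.1; Protocol 5.1 agrees).**
- Cohort 1: "Subjects will return to the CRU for an end-of-study (EOS) visit on Day 21". Protocol Table 2.1 and SAP Table 1.1 have no column between 24 h and 480 h, and Protocol 5.1.2 describes the on-study period as a treatment period and an EOS visit only.
- Cohort 2: "Subjects will return to the CRU for follow-up visits on Days 5", 9 and 16, then EOS on Day 22.
- Cohorts 3 and 4: "Patients will return to the CRU for follow-up visits on Days 4", 8 and 15, then EOS on Day 21.

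**How measurements become AEs.** Protocol 8.6.2, below Table 8.3: "Record as an AE any laboratory test value that (1) is confirmed by repeat and the investigator considers clinically significant", or if the value leads to treatment, discontinuation or a change of study drug. Protocol 8.6.4 has a similar rule for vital signs.

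**The concern.** A laboratory or vital-sign abnormality can be recorded as an AE only if somebody measures it. The nominal AE window has about the same length in all cohorts, but after the first day the number of measurements inside it differs. The TEAE percentages therefore partly reflect how often subjects were seen.

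Safety and tolerability in healthy subjects and in patients with renal impairment is the first primary objective. Side-by-side percentages by cohort, plus an overall column, are the main tabulated AE result. Cohort 1 is up to 8 of the 16 healthy subjects and up to 8 of all 32. Protocol 10.6 foresaw a breakdown by cohort and treatment; SAP 10.1.11.2 keeps cohort only, so the cohort columns are what readers will compare.

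The unobserved interval is also not free of exposure. Protocol 3.4.3 reports an FD003 half-life of 90 to 125 hours.

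**Working it through.** **1. Scheduled visits after discharge**, counted from Protocol 5.1, Tables 2.1, 2.2, 2.3.1 and 2.3.2, and SAP Tables 1.1 to 1.3:

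| Cohort | Intermediate visits | EOS | Total |
|---|---|---|---|
| 1 | 0 | 1 | 1 |
| 2 | 3 | 1 | 4 |
| 3 and 4 | 3 | 1 | 4 |

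Cohorts 3 and 4 also have a 32 h sample. Cohort 2 also has a second intensive in-unit day after dose 2.

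**2. What is measured at the intermediate visits.** Vital signs, AE collection, and haematology and chemistry. The three laboratory panels are clear for Cohorts 3 and 4 (Protocol Table 2.3.1). For Cohort 2 the visits are certain, but the laboratory row did not survive extraction well enough to confirm a panel at each. No physical examination is scheduled at these visits, so examination findings are not affected.

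**3. Illustration of unequal detection.** The documents give no rate, duration or onset pattern, so these are assumptions: onset uniform from Day 2 to Day 21 (19 days), duration d days, visits on their nominal days, and a finding detected only if present at a visit.

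- Cohort 1 (visit on Day 21): P = min(d, 19)/19.
- Cohorts 3–4 (visits on Days 4, 8, 15, 21; gaps of 2, 4, 7 and 6 days counted from Day 2): P = [min(2,d) + min(4,d) + min(7,d) + min(6,d)]/19.

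| d | Cohort 1 | Cohorts 3–4 | Ratio |
|---|---|---|---|
| 1 | 1/19 = 5.3% | 4/19 = 21.1% | 4.0 |
| 3 | 3/19 = 15.8% | (2+3+3+3)/19 = 57.9% | 3.7 |
| 7 | 7/19 = 36.8% | 19/19 = 100% | 2.7 |
| 14 | 14/19 = 73.7% | 100% | 1.4 |
| 19 or more | 100% | 100% | 1.0 |

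Cohort 2, with every day shifted by one (onset Day 3 to Day 22; visits on Days 5, 9, 16, 22), gives the same values as Cohorts 3–4.

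**4. Effect on the pooled figure.** With 8 per cohort, Cohort 1 has weight 8/32 = 0.25. For d = 3: 0.25 × 3/19 + 0.75 × 11/19 = 9/19 = 47.4%, against 57.9% had all cohorts been followed alike. For d = 14: 0.25 × 14/19 + 0.75 = 93.4%, against 100%.

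**5. Exposure in the gap.** Assuming mono-exponential FD003 decline, the share of total exposure between 24 h and 480 h is 2^(−24/t½) − 2^(−480/t½). For t½ = 90 h: 0.831 − 0.025 = 0.81. For t½ = 125 h: 0.875 − 0.070 = 0.81.

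**6. Precision.** The exact 95% confidence interval is 0 to 36.9% for 0 of 8 and 0.3 to 52.7% for 1 of 8.

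**The case against.** The strongest case against is that nothing in the plan formally compares cohorts. Protocol 3.7 says that results are interpreted descriptively only, and the primary safety objective sets VFI against Iohexol, not healthy subjects against renal patients. Cohorts also differ in renal function, iohexol, albumin and number of VFI doses, and with 8 subjects each no percentage is precise. Symptomatic events can be recalled at Cohort 1's EOS visit. The first-in-human study reported mainly local, itching and gastrointestinal events, with no clinically relevant laboratory or vital-sign effects. Every AE is listed by subject, SAP listings carry study day, and laboratory and vital-sign summaries are by visit, so those are not distorted.

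Most of this stands as a limit on size. It does not remove the point: descriptive percentages will still be read across columns, and nothing in SAP 10.1.11.2 warns that the later period was observed unequally.

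Three stronger readings are tempting, and the documents do not support them.
- *VFI will look safer in healthy subjects than in renal patients.* There is no pooled healthy column. Cohort 2 is healthy and has the same number of follow-up visits as Cohorts 3–4, while its second dose and second in-unit day can raise its count. The net direction is unknown.
- *Detection differs by a known factor of about 3 to 4.* The ratio depends on the assumed duration and vanishes at 19 days. Presence at a visit is also not yet an AE, because confirmation and clinical significance, or an action taken, are required.
- *A 24 h table should be the only basis for comparing cohorts.* With an FD003 half-life of 90 to 125 h, that would set aside the period holding most of the exposure. Nor is the first 24 h observed identically: patients at the University of Alabama site leave the unit after the 12 h sample.

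**Conclusion.** The point holds as a limited problem of ascertainment. The imbalance of one scheduled post-discharge visit against four is certain from both documents. It can lower Cohort 1's TEAE rate and the pooled rate for transient or silent laboratory and vital-sign events after 24 h; examination findings are unaffected and symptomatic events probably less so. How much it does so cannot be computed from the documents. The percentages above rest on uniform onset, fixed duration and nominal visit days, and only show that the effect could be material for short-lived findings and small for long-lasting ones. Because the display serves a primary objective and the remedy is a matter of tabulation, the change is worth making.

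**What to change.** In SAP 10.1.11.2 and the Table 14.3.1 series, keep the full-period TEAE tables and add a summary split by onset period:

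- **(a)** From the first VFI dose to 24 h, or to dose 2 in Cohort 2 if that comes first, by cohort and overall. The dose 2 condition is needed because Protocol Table 2.5 lets dose 2 fall at 24 h ± 1 h.
- **(b)** After that point, by cohort, with Cohort 1 shown separately and an additional pooled column for Cohorts 2–4.

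Onset clock time is not among the AE items listed in Protocol 9.1, and SAP 10.1 derives study day from dates. If it is not captured, define the split by onset date: state one rule for Day 2 onsets in all cohorts and, in Cohort 2, whether the event began before or after dose 2.

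Footnote the full-period tables with the number of scheduled post-24 h contacts per cohort. Footnote table (a) to say that University of Alabama patients are outside the unit from 12 h to 24 h.

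Cost: additional programming only, with no change to visits or to the Safety Population. The small downside is fewer events per table.

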10.1.11.3 Clinical Laboratory Assessments

Clinical laboratory results will be included in the reporting of this study for hematology, coagulation, serum chemistry and urinalysis.

Absolute and change from baseline for each parameter of continuous clinical laboratory values (chemistry, hematology and urinalysis) will be summarized by cohort at each visit.

The baseline laboratory test results for clinical assessment for a particular test will be defined as the last measurement prior to the initial dose of study drug. Any unscheduled measurements will only be displayed in the listings

Other laboratory tests such as urine drugs of abuse, serology tests & pregnancy test and follicle-stimulating hormone (FSH) will also be displayed in listings.

Laboratory data will be listed by subject at each visit. Clinical laboratory values that are outside of the normal ranges values will be flagged in the data listing. Clinical significance will be indicated in the data listing.

10.1.11.4 Vital Signs

Vital signs data including pulse oximetry will be listed by subject at each visit and time point. Absolute and change from baseline vital signs values will be summarized by cohort at each visit and time point. Any unscheduled measurements will only be displayed in the listings.

Clinical significance will be indicated in the data listing. Out of range vital signs values will be flagged in the data listing.

10.1.11.5 Electrocardiograms

Electrocardiogram data will be listed by subject at each visit and time point.

Observed value and change from baseline of ECG parameters (HR, RR, PR, QRS, and QT and QT interval corrected for HR using Fridericia's formula (QTcF) intervals) will be summarized by cohort at each nominal timepoint. Any unscheduled measurements will only be displayed in the listings. Clinical significance will be indicated in the data listing.

10.1.11.6 Physical Examinations

Physical examination findings will be presented in a subject listing.

10.1.11.7 Concomitant Medications

Concomitant medications will be coded using the World Health Organization Drug Dictionary (WHODD, Version March 2016 or later) and classified according to anatomical therapeutic chemical code levels 2 (therapeutic sublevel) and 4 (chemical sublevel).

Concomitant medications: are defined as those medications with a start date on or after the start of the infusion of study drug or started prior to the start of the infusion of study drug and were continued after the start of the infusion of study drug.

Concomitant medications will be summarized descriptively using frequency tables by ATC class and preferred name by cohort and overall on the Safety Population. Concomitant medication data will be listed.

10.1.12 Sample Size

Approximately 32 subjects/patients will be enrolled in 4 cohorts consisting of up to 8 subjects/patients each.

The sample size in this study is representative of Phase 2b studies of this type. Power calculations were not used to derive the sample size.

10.1.13 Interim Analysis

No interim analyses are planned for this study. For details of Interim Safety Data Review, please refer to the protocol Section 5.1.1.

10.1.14 General Conventions for Tables, Listings and Figures

For summary tables, unless otherwise specified, the number of decimal places provided in the SAS output will be based on the accuracy of the least accurate value in the raw data as follows:

n	integer
Arithmetic mean	1 decimal place more than the least accurate number in the raw data
SD	2 decimal place more than the least accurate number in the raw data
CV (%)	2 decimal places
Geometric mean	1 decimal place more than the least accurate number in the raw data
Geometric CV (%)	2 decimal places
Median	1 decimal place more than the least accurate number in the raw data
Minimum	same number of decimal places as raw data
Maximum	same number of decimal places as raw data
Confidence interval	same number of decimals as the associated statistic
Geometric mean ratio	2 decimal places

11 TABLES, FIGURES, AND LISTINGS

Table/Figure Number	Table/Figure Name
Section 14.1	Demographic and Subject Characteristics Data Summaries
Table 14.1.1	Summary of Subject Disposition (All Enrolled)
Table 14.1.2	Summary of Demographic Data (Safety Population)
Table 14.1.3	Summary of Concomitant medication (Safety Population)
Section 14.2	Pharmacokinetic Data Summaries
Table 14.2.1.1	Summary of Plasma concentration of FD001 and FD003 (PK Full Population)
Table 14.2.1.2	Summary of plasma pharmacokinetic parameters of FD001 and FD003 (PK Evaluable Population)
Table 14.2.2.1	Summary of urinary excretion of FD001 and FD003 (PK Full Population)
Table 14.2.2.2	Summary of urine pharmacokinetic parameters of FD001 and FD003 (PK Evaluable Population)
Figure 14.2.1	Mean (+SD) Plasma Concentrations-Time Profile (PK Full Population)
Figure 14.2.2	Mean (+SD) Urine Cumulative Amount Excreted -Time Profile (PK Full Population)
Section 14.2.3	Pharmacodynamic Data Summaries
Table 14.2.3.1	Summary of Pharmacodynamic Parameter- Plasma volume (PD Evaluable Population)
Figure 14.2.3.1	Scatter plot of Pharmacodynamic Parameter Plasma volume estimated using FAST PV and Nadler's Formula (PD Evaluable Population)
Table 14.2.3.2	Summary of Pharmacodynamic Parameter glomerular filtration rate (PD Evaluable Population)

Table 14.2.3.3	Summary of glomerular filtration rate estimated using the MDRD, CKD-EPI, and Cockcroft-Gault equations (PD Evaluable Population)
Figure 14.2.3.2	Scatter plot of Pharmacodynamic Parameter glomerular filtration rate estimated using FAST PV and Iohexol mGFR (PD Evaluable Population)
Figure 14.2.3.3	Histogram for the magnitude of difference (PV using FAST PV - PV estimated using Nadler's formula) (PD Evaluable Population)
Figure 14.2.3.4	Bland-Altman plot: FAST VFI vs Iohexol GFR(PD Evaluable Population)

Section 14.3

Safety Data Summaries

Section 14.3.1

Displays of Adverse Events

Table 14.3.1.1

Overall Summary of Treatment-Emergent Adverse Events (Safety Population)

Table 14.3.1.2

Summary of Treatment-Emergent Adverse Events by System Organ Class and Preferred Term (Safety Population)

Table 14.3.1.3

Summary of Treatment-Emergent Adverse Events by Severity Grade (Safety Population)

Table 14.3.1.4

Summary of Treatment-Emergent Adverse Events by Relationship to Study Drug (Safety Population)

Section 14.3.2

Listings of Deaths, Other Serious and Certain Significant Adverse Events

Table 14.3.2.1

Subject Listing of Death (Safety Population)

Table 14.3.2.2

Subject Listing of Serious Adverse Events (Safety Population)

Table 14.3.2.3

Subject Listing of Adverse Events Leading to Study Discontinuation (Safety Population)

Section 14.3.3

Narratives of Deaths, Other Serious and Certain Significant Adverse Events

Section 14.3.4

Abnormal Laboratory Value Listing

Table 14.3.4.1	Listing of Abnormal Laboratory Results (Safety Population)
Section 14.3.5	Additional Safety Data Summaries
Table 14.3.5.1	Absolute and Change from Baseline for Clinical Laboratory Parameters by cohort (Safety Population)
Table 14.3.6.1	Absolute and Change from Baseline for Vital Signs (Safety Population)
Table 14.3.7.1	Absolute and Change from Baseline for ECG parameters (Safety Population)
Listing Number	Listing Name
Section 16.2.1	Discontinued Subjects
Listing 16.2.1	Subject Disposition (All Enrolled)
Section 16.2.2	Protocol Deviations
Listing 16.2.2	Protocol Deviations (All Enrolled)
Section 16.2.3	Subjects Excluded from Analysis
Listing 16.2.3	Analysis Sets and reason for exclusion (All Enrolled)
Section 16.2.4	Demographic Data
Listing 16.2.4.1	Demographic Data (Safety Population)
Listing 16.2.4.2	Physical measurements (Safety Population)
Listing 16.2.4.3	Inclusion/Exclusion Criteria (Safety Population)
Listing 16.2.4.4	Medical and Surgical History (Safety Population)
Listing 16.2.4.5	Concomitant Medications (Safety Population)
Section 16.2.5	Compliance and/or Drug Concentration Data
Listing 16.2.5.1	Study Drug Dosing Record (Safety Population)
Listing 16.2.5.2	Individual Plasma Concentrations (PK full Population)
Listing 16.2.5.3	Individual Urine Concentrations (PK full Population)

Figure 16.2.5.1	Plots of Plasma Concentration vs Time (PK full Population)
Figure 16.2.5.2	Plots of Urine Cumulative Amount Excreted vs Time (PK full Population)
Section 16.2.6	Individual Pharmacokinetic and Pharmacodynamic Data
Section 16.2.6.1	Individual Pharmacokinetic Response Data
Listing 16.2.6.1.1	Individual plasma PK Parameters (PK evaluable Population)
Listing 16.2.6.1.2	Individual urine PK Parameters (PK evaluable Population)
Section 16.2.6.3	Individual Pharmacodynamic Response Data
Listing 16.2.6.3.1	Individual PD Parameters (PD evaluable Population)
Section 16.2.7	Adverse Event Listings
Listing 16.2.7.1	All Adverse Events (Safety Population)
Section 16.2.8	Individual Laboratory Measurements by Subject
Listing 16.2.8.1	Clinical Laboratory Data by Category (Safety Population)
Listing 16.2.8.2	Abnormal Laboratory Results by Category (Safety Population)
Listing 16.2.8.3	Vital Signs (Safety Population)
Listing 16.2.8.4	Electrocardiogram Results (Safety Population)
Listing 16.2.8.5	Physical Examination Findings (Safety Population)
Listing 16.2.9.1	Investigator comments (Safety Population)
